16.13. Suspension or Early Termination of Clinical Study	
16.13.1. Investigational Center Suspension or Termination	
16.13.2. Subject Follow-Up In Case of Termination	
16.14. Study Close Out	89
16.15. Publication and Use of Information	89

Page 9 of 97

17.	References	90
18.	Appendices	90
18.	1. Appendix A: Contact Information	
18	8.1.1. Names and Addresses of Investigational Centers	91
18	8.1.2. Sponsor's and Local Sponsor's Staff Contact	91
18.	2. Appendix B	92
	3. Appendix C: Relevant Qualification Document(S) Of The Sponsor/Local	
Spo	onsor(Agent)	93
18.	4. Appendix D: Informed Consent Form Template	93
19.	Version History	93

10768467DOC Version C

Page 10 of 97

2. Glossary

Term	Definition
A1C	Glycosylated hemoglobin
AE	Adverse Event
ARD	Absolute Relative Difference
BG	Blood Glucose
BMI	Body Mass Index
CEC	Clinical Events Committee
CFDA	China Food and Drug Administration
CGM	Continuous Glucose Monitoring
CGMS	Continuous Glucose Monitoring System
CIP	Clinical Investigation Plan
СТА	Clinical Trial Approval
CV	Curriculum Vitae
DKA	Diabetic Ketoacidosis
EC	Ethics Committee
eCRF	Electronic Case Report Form
EGA	Error Grid Analysis
ER	Emergency Room
EOS	End of Study
FST	Frequent Sample Testing
Hct	Hematocrit

10768467DOC Version C

Page 11 of 97

Term	Definition
ICF	Informed Consent Form
IFU	Instructions for Use
ISIG	Interstitial Signal
IV	Intravenous
MARD	Mean Absolute Relative Difference
NMPA	National Medical Products Administration
OC-RDC	Oracle Clinical Remote Data Capture
PC	Personal Computer
POC	Point of Care
QC	Quality Control
SAE	Serious Adverse Event
SGV	Sensor Glucose Value
SID	Subject Identification
SMBG	Self-Monitoring of Blood Glucose
SQ	Subcutaneous
UADE	Unanticipated Adverse Device Effect
USB	Universal Serial Bus
YSI [™] *	Yellow Springs Instrument

CONTOUR™* is a registered trademark of Ascensia Diabetes Care.

YSI™* is a trademark of Xylem Inc. or one of its subsidiaries.

© 2018 Medtronic. All rights reserved. Medtronic, Medtronic logo and Further, Together are trademarks of Medtronic. **Third party brands are trademarks of their respective owners.

All other brands are trademarks of a Medtronic company.

10768467DOC Version C Page 12 of 97

3. Synopsis

Title	A Pivotal Study to Evaluate Guardian [™] Connect CGM System Performance in China			
Clinical Study Type	Pivotal study			
Sponsor	Medtronic MiniMed, Inc. ("Medtronic") [name] [contact]			
Local Sponsor(Agent)	Medtronic (Shanghai) Management Co., Ltd. [name]			
Indication under investigation	Type 1 diabetes, Type 2 diabetes			
Devices	 Investigational Devices: Guardian™ Connect App (CSS7200) - software app loaded onto iOS device Guardian™ Sensor (3) (MMT-7020) One-press Serter (MMT-7512) Guardian™ Connect Transmitter (MMT-7821) GST3C/4C Dock (T8381) GST Download Utility Software (M973132) USB cable and wall-powered adaptor for GST3C/4C Dock (MMT-7747) Tester (MMT-7736L) Charger (MMT-7715) 			

10768467DOC Version C Page 13 of 97

	Non-Investigational Devices:				
	 Ascencia CONTOUR™* PLUS Blood Glucose Meter (7619)-referred to as the CONTOUR™* study meter in this protocol 				
	 Ascencia CONTOUR™* PLUS Blood Glucose Test Strips (7662) 				
	Ascencia CONTOUR™* PLUS Control Solution (7680)				
Category of investigational medical device	Class III				
Class III medical devices requiring Clinical Trial Approval (CTA)	No				
Purpose	The primary purpose of this study is to demonstrate the performance and safety of the Guardian™ Sensor (3) over 170 hours (7 days) when inserted in the abdomen used in subjects age 14 – 75 years with the Guardian™ Connect System. The secondary purpose of this study is to collect data that will be used to characterize the accuracy of the Guardian™ Sensor (3) when used with the following systems: • MiniMed™ 600G/700G series insulin pump systems				
	Envision system				
Objective(s)	The primary objective of the study is to demonstrate the accuracy of Guardian™ Sensor (3) when used over a period of 7 days with the Guardian™ Connect System. The secondary objective of the study is to collect data that will be used to characterize the accuracy of the Guardian™ Sensor (3) when used with the following systems:				
	 MiniMed™ 600G/700G series insulin pump systems 				
	Envision system				
Study Design	This study is a multi-center, prospective single-arm design without controls. Up to 72 subjects will be enrolled in order to have approximately 60 subjects complete the study. Three investigational centers in China will be used during this study.				
	During the study, each subject will be randomly assigned to one day of the Yellow Springs Instrument (YSI™*) frequent sample testing (FST) (Day 1,				

10768467DOC Version C Page 14 of 97

	3-5, or 7). Subjects will wear two Guardian™ Sensor (3)s each connected to a Guardian™ Connect transmitter for approximately 7 days (one which will be paired to the Guardian Connect app and the other will function as a glucose recorder.). The Guardian Sensor (3)s will be worn in the abdomen area and self-inserted by the subject on same side or opposite sides.
	On the evening prior to FST, subjects will be asked to fast for approximately 12 hours and adjust their insulin and medications according to routine care (for example as they would do for fasting lipid panel). Subjects may fast for shorter period of time based on investigator discretion.
	The subject should be in fasting status upon arrival at hospital to start FST process. The feeding protocol may be modified based on investigator discretion.
	The duration of FST will be approximately 7 hours.
	During the study, subjects will continue with their current diabetes regimen independent of the study devices. Subjects will be instructed by the investigational center that they are not to use the study devices (except for the CONTOUR™* study meter) for the management of their diabetes. The CONTOUR™* study meter may be used for treatment decisions and calibration of Guardian™ Sensor (3).
	Calibration at Home: Calibration at home will be required to be 3-4 times spread throughout the day for the Guardian™ Connect app.
	Calibration should also be performed if the Guardian™ Connect app prompts for calibration (i.e., Smart calibration feature). NOTE: Subject will be instructed to minimize the delay time between prompt and calibration.
	Fingerstick Testing: Fingerstick testing will be recommended to be a minimum of 4 times spread throughout the day. Subjects should test prior to and following meals and at bedtime.
Random Assignment	Subjects will be randomly assigned to one of the following days for the inclinic YSI™* FST: Day 1, 3-5, or 7.
Sample Size and Investigational Centers	Up to 72 subjects will be enrolled in order to have approximately 60 subjects complete the study. Three investigational centers in China will be

10768467DOC Version C Page 15 of 97

	used during this study. A minimum of 12 subjects and a maximum of 30 subjects will be enrolled at each investigational center.			
	Diabetes cohorts based on insulin requirement			
	 Minimum of 20 type 2 insulin requiring 			
	 Minimum of 25 type 2 non-insulin requiring 			
Duration	The study is anticipated to last no more than 12 months from investigational center initiation to finalization of all data entry and monitoring procedures. The subject's maximum participation from study start to completion is approximately 3 weeks (including replacement sensor wear and repeat in-clinic procedures).			
Inclusion/Exclusion Criteria	Inclusion Criteria:			
	1. Subject is 14 - 75 years of age at time of screening			
	Subject has a clinical diagnosis of type 1 or 2 diabetes as determined via medical record or source documentation by an individual qualified to make a medical diagnosis			
	Subject has adequate venous access as assessed by investigator or appropriate staff			
	 Subject is willing to follow the study procedures and willing to come to study visits. 			
	Exclusion Criteria:			
	 Subject will not tolerate tape adhesive in the area of Guardian™ Sensor placement as assessed by qualified individual. 			
	2. Subject has any unresolved adverse skin condition in the area of study device or device placement (e.g., psoriasis, rash, Staphylococcus infection)			
	3. Subject is actively participating in an investigational study (drug or device) wherein they have received treatment from an investigational study (drug or device) in the last 2 weeks			
	4. Subject is female and has a positive pregnancy screening test			
	5. Females of child bearing age and who are sexually active should be excluded if they are not using a form of contraception deemed reliable by investigator			

10768467DOC Version C Page 16 of 97

	Subject is female and plans to become pregnant during the course of the study				
	7. Subject has a hematocrit (Hct) lower than the normal reference range				
	8. Subject may not be on the research staff of those performing this study				
Study Timeline:	The subject's participation from study start to completion is approximately 1 – 3 weeks (including replacement sensor wear and repeat in-clinic procedures). Additional rescheduled visits could occur if Guardian™ Sensor (3)s dislodge and new Guardian™ Sensor (3)s must be re-inserted (See Replacement Sensors, Section 9.6)				
	Visit 1: Consent and Screening				
	Visit 2: Random Assignment				
	 Visit 1 and 2 can be combined, however all eligibility criteria on Visit 1 should be met, including review of Hct prior to Visit 2. 				
	 Visit 1 and Visit 2 should be no more than 2 weeks apart. 				
	Visit 3: Study & Device Training				
	 Two Guardian™ Sensor (3)s each connected to a Guardian™ Connect transmitter Dispense Patient Log Sheet if CONTOUR™* study meter BG software and cable is not accessible at time of the study start 				
	Visit 4: YSI™* FST				
	 Study and device training (Day 1 subjects who have not already received study and device training from Visit 3) 				
	 Subjects will undergo one YSI™* FST on any one of the following sensor wear days: 				
	■ Day 1				
	■ Day 3 – 5				
	■ Day 7				
	Visit 5: End of Study (EOS) Visit				
	 Guardian™ Connect transmitters removed (Please note that the subject should target wearing the device for 170 hours or longer from time of insertion) 				

10768467DOC Version C Page 17 of 97

- Investigational center staff will:
 - Download the Guardian™ Connect transmitters data from GST Download Utility Software following completion of the study devices wear
 - Download subject's CONTOUR™* study meter BG values
 - Collect subject's Patient Log Sheet if CONTOUR™* study meter BG software and cable is not accessible at time of the study start
 - Provide CONTOUR™* study meter and Guardian™ Connect transmitter data to sponsor
- Return study devices
- Subject complete questionnaires

Guidelines for Combining Visits:

- All subjects meeting eligibility criteria:
 - Visit 1 and 2 can be combined, however all eligibility criteria on Visit 1 should be met, including review of Hct prior to Visit 2.
- Subjects randomly assigned to FST Day 1
 - Subjects doing FST on Day 1 may combine Visit 2 and Visit 3 as long as they are able to perform Visit 4 FST in the second half of FST day.
 - For example, subject does Visit 1 and 2 in the morning and performs Visit 3 in the afternoon. Subjects come in the next day for Visit 4 in the morning within approximately 26 hours from time of insertion.
- Subjects randomly assigned to FST Day 3-5
 - May combine Visit 2 and Visit 3
- Subjects randomly assigned to FST Day 7
 - May combine Visit 2 and Visit 3
 - May combine Visit 4 and Visit 5 as long as the subject has worn N=170 hours.

10768467DOC Version C Page 18 of 97

Device Deficiencies:	Subject and investigational center reports of device deficiencies will be collected by electronic Case Report Forms (eCRF) for device troubleshooting and device complaints. For additional information, see Section 13.				
Subject Stopping Rules	The subject will stop the study if there is an unanticipated adverse device effect (UADE).				
Stopping Rules Entire Study	The study will stop if there is an UADE.				
Repeat Rules for In-Clinic Procedures	• Concurrent failure of both the primary and back-up YSI™* instruments (if applicable) during YSI™* FST.				
	 If a sensor connecting to the transmitter which pairs to the Guardian Connect app fails/dislodges prior to YSI™* FST or within a duration of 5 hours YSI™* FST, both sensors will be replaced per sponsor's recommendation (For additional information, see Section 9.6). 				
	 If subject experiences unresolved intravenous (IV) occlusions during YSI™* FST or within a duration of 5 hours YSI™* FST requiring fingerstick measurements for a prolonged time period, the FST procedures may be rescheduled per sponsor recommendation. 				
Statistical Analysis for Endpoints and Hypothesis:	Primary Endpoint Guardian™ Sensor (3) connected to a Guardian™ Connect transmitter and paired to the Guardian Connect app will be the primary sensor.				
	1a) Sensor values from primary sensor will be compared to YSI ^{™*} plasma glucose values during YSI ^{™*} FSTs. A within 20% agreement rate (±20 mg/dL (1.1 mmol/L) when Reference BG less than or equal to (≤) 80 mg/dL (4.4 mmol/L) between Guardian [™] Sensor (3) values and YSI ^{™*} plasma glucose values during YSI ^{™*} FST days defined as p will be evaluated against the null Hypothesis:				
	H0: p ≤ 60%				
	H1: p > 60%				
	1b) Sensor values from primary sensor will be compared to YSI™* plasma glucose values during YSI™* FSTs. A mean rate in Zone A+B of Consensu Error Grid between Guardian Sensor (3) values and YSI™* plasma glucose values during YSI™* FST days defined as p will be evaluated against the null Hypothesis:				
	H0: p ≤ 90%				
	H1: p > 90%				
	1c) Sensor values from primary sensor will be compared to YSI™* plasma				

10768467DOC Version C Page 19 of 97

glucose values during YSI™* FSTs. A mean rate in Zone A+B of Clarke Error Grid between Guardian Sensor (3) values and YSI™* plasma glucose values during YSI™* FST days defined as p will be evaluated against the null Hypothesis:

H0: p ≤ 90%

H1: p > 90%

1d) Sensor values from primary sensor will be compared to YSI^{TM*} plasma glucose values during YSI^{TM*} FSTs. A mean absolute relative difference (MARD) between Guardian Sensor (3) values and YSI^{TM*} plasma glucose values during YSI^{TM*} FST days defined as μ will be evaluated against the null Hypothesis:

H0: μ ≥ 20%

H1: μ < 20%

Statistical testing

At 1a), 1b), and 1c) evaluation criteria, one proportion Z test will be used for the analysis of the primary endpoint. The 97.5% lower confidence limit of the agreement rate, the mean rate in Zone A+B of Consensus Error Grid, and the mean rate in Zone A+B of Clarke Error Grid will be tested against corresponding threshold, respectively.

At 1d) evaluation criteria, one sample T test will be used and the 97.5% upper confidence limit of the MARD will be tested against corresponding threshold.

The study will be considered as a success only when the four evaluation criteria (1a), 1b), 1c), and 1d)) meet the pre-defined thresholds.

Other descriptive endpoints

- Alert performance will be characterized throughout hypoglycemia and hyperglycemia glucose ranges.
- 20% agreement rate and MARD will be summarized descriptively by FST days (Day 1, 3-5 and 7).
- Precision analysis including Absolute Relative Difference (ARD), and 20% agreement rate (±20 mg/dL (1.1 mmol/L) when Reference BG less than or equal to (≤) 80 mg/dL (4.4 mmol/L)) will be performed.

10768467DOC Version C Page 20 of 97

 The number of actual calibrations performed per day by study subjects will be tabulated and presented.

Safety

For Safety analysis, no formal hypothesis testing will be performed. Descriptive analytics will be used to summarize safety events. Safety events which will be characterized include:

- Skin assessment of Guardian™ Sensor (3) insertion sites
- All adverse events (AEs) to include but not limited to:
 - Device Related AE
 - Procedure Related AE
 - Serious Adverse Event (SAE)
 - Serious Adverse Device Effects (SADE)
 - o UADE
 - o Severe Hypoglycemia
 - Diabetic Ketoacidosis (DKA)

Device Deficiencies

Descriptive summary will be used to characterize device deficiencies.

Subject Feedback

Descriptive summary will be used to characterize study questionnaire results. The questionnaire will use a Likert scale rating to assess their GuardianTM Sensor (3) experience.

10768467DOC Version C

Page 21 of 97

4. Introduction

4.1. Background

Medtronic Continuous Glucose Monitoring Systems (CGMS) measure subcutaneous (SQ) glucose continuously over various ranges of time. Medtronic's newest generation SQ glucose sensor (the Guardian™ Sensor (3)) glucose sensor was approved by the United States Food and Drug Administration (FDA) in September 2016 as part of the MiniMed™ 670G System. The Guardian Sensor (3) is designed to be used with compatible Medtronic monitors, transmitters, or recorders to help users manage their diabetes.

The Guardian[™] Sensor (3) glucose sensor design is similar to the Sof-sensor[™] glucose sensor which is approved by National Medical Products Administration (NMPA, formerly CFDA). The Guardian[™] Sensor (3) glucose sensor connects to a glucose sensor transmitter (Guardian[™] Connect transmitter). A personal mobile device running the Guardian[™] Connect app is the monitoring device used in the Guardian[™] Connect System. Although the Guardian[™] Connect System has been previously evaluated during clinical investigation performed in the United States, testing with Chinese subjects is necessary to support NMPA approval of the Guardian[™] Connect System.

For purposes of this study, subjects will wear two Guardian[™] Sensor (3) glucose sensors. Subjects will manage their diabetes independent of the Guardian[™] Sensor (3) glucose sensor values. During this time, venous blood glucose (BG) concentrations will be measured periodically by a reference method; these values will be compared to sensor glucose values (SGVs) in order to determine sensor accuracy.

The study is designed to demonstrate the performance and safety of the GuardianTM Sensor (3) glucose sensor when inserted in the abdomen used in Chinese subjects age 14-75 years. The data gathered is intended to support over 170 hours (7 days) of use with the GuardianTM Connect System. In addition, the study will collect data that will be used to model the accuracy of the GuardianTM Sensor (3) when used with the MiniMedTM 600G/700G series insulin pump systems and the Envision system.

Accuracy will be calculated based on comparing calibrated glucose sensor values to a "gold standard" (Yellow Springs Instrument [YSI™*™] plasma glucose values) in subjects during YSI™* frequent sample testing (FST). YSI™* glucose analyzers have been recognized standards for the measurement of BG and will be utilized across the investigational centers for the tests.

4.2. Purpose

The primary purpose of this study is to demonstrate the performance and safety of the GuardianTM Sensor (3) over 170 hours (7 days) when inserted in the abdomen used in subjects age 14 - 75 years with the GuardianTM Connect System.

The secondary purpose of this study is to collect data that will be used to characterize the accuracy of the Guardian™ Sensor (3) when used with the following systems:

- MiniMed[™] 600G/700G series insulin pump systems
- Envision system

10768467DOC Version C

5. Objectives and Endpoints

5.1. Objectives

5.1.1. Primary Objective(s)

The primary objective of the study is to demonstrate the accuracy of Guardian™ Sensor (3) when used over a period of 7 days with the Guardian™ Connect System.

The secondary objective of the study is to collect data that will be used to characterize the accuracy of the Guardian™ Sensor (3) when used with the following systems:

- MiniMed[™] 600G/700G series insulin pump systems
- Envision system

5.2. Endpoints

5.2.1. Primary Endpoints

Guardian™ Sensor (3) connected to a Guardian™ Connect transmitter and paired to the Guardian Connect app will be the primary sensor.

1a) Sensor values from primary sensor will be compared to YSI™* plasma glucose values during YSI™* FSTs. A within 20% agreement rate (±20 mg/dL (1.1 mmol/L) when Reference BG less than or equal to (≤) 80 mg/dL (4.4 mmol/L) between Guardian™ Sensor (3) values and YSI™* plasma glucose values during YSI™* FST days defined as p will be evaluated against the null Hypothesis:

H0: p ≤ 60%

H1: p > 60%

1b) Sensor values from primary sensor will be compared to YSI™* plasma glucose values during YSI™* FSTs. A mean rate in Zone A+B of Consensus Error Grid between Guardian Sensor (3) values and YSI™* plasma glucose values during YSI™* FST days defined as p will be evaluated against the null Hypothesis:

H0: p ≤ 90%

H1: p > 90%

10768467DOC Version C

Page 23 of 97 Medtronic

1c) Sensor values from primary sensor will be compared to YSI™* plasma glucose values during YSI™* FSTs. A mean rate in Zone A+B of Clarke Error Grid between Guardian Sensor (3) values and YSI™* plasma glucose values during YSI™* FST days defined as p will be evaluated against the null Hypothesis:

H0: p ≤ 90%

H1: p > 90%

1d) Sensor values from primary sensor will be compared to YSI^{TM*} plasma glucose values during YSI^{TM*} FSTs. A mean absolute relative difference (MARD) between Guardian Sensor (3) values and YSI^{TM*} plasma glucose values during YSI^{TM*} FST days defined as μ will be evaluated against the null Hypothesis:

H0: μ ≥ 20%

H1: μ < 20%

Statistical testing

At 1a), 1b), and 1c) evaluation criteria, one proportion Z test will be used for the analysis of the primary endpoint. The 97.5% lower confidence limit of the agreement rate, the mean rate in Zone A+B of Consensus Error Grid, and the mean rate in Zone A+B of Clarke Error Grid will be tested against corresponding threshold, respectively.

At 1d) evaluation criteria, one sample T test will be used and the 97.5% upper confidence limit of the MARD will be tested against corresponding threshold.

The study will be considered as a success only when the four evaluation criteria (1a), 1b), 1c), and 1d)) meet the pre-defined thresholds.

5.2.2. Other Descriptive Endpoints

- Alert performance will be characterized throughout hypoglycemia and hyperglycemia glucose ranges.
- 20% agreement rate and MARD will be summarized descriptively by FST days (Day 1, 3-5 and 7).
- Precision analysis including Absolute Relative Difference (ARD), and 20% agreement rate (±20 mg/dL (1.1 mmol/L) when Reference BG less than or equal to (≤) 80 mg/dL (4.4 mmol/L)) will be performed.
- The number of actual calibrations performed per day by study subjects will be tabulated and presented.

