9.2.4.1. Overview General Study Procedures

Investigational center staff will:

- Provide subject with the opportunity to bring up study-related questions and concerns
- Ask subject about the occurrence of AEs
 - Record AEs on the appropriate eCRF, if subject reports health status changes that result in a new medical condition or deterioration of an existing medical condition, such as sickness or glycemic problems.
- Ask subject about device deficiencies
- Prepare all study devices following the instructions in the instructions for use (IFU) including the following:
 - Synchronize time on Guardian™ Connect app and CONTOUR™* study meter using investigational center's designated study clock
 - Synchronize study laptop computer at the investigational center using investigational center's designated study clock
 - Fully charge the transmitter(s) prior to distribution to study subject
- Perform applicable quality control (QC) testing (CONTOUR™* study meter). Shake control solution bottle well prior to use. QC should be performed:
 - o prior to dispensing a CONTOUR™* study meter
 - o any time additional strips are given to the subject
- Instruct trained subject to self-insert Guardian[™] Sensor (3)s into the abdomen area and perform connection of Guardian[™] Sensor (3)s to the Guardian[™] Connect transmitters. It is up to investigator's discretion on which Guardian[™] Sensor (3) will be connected to the Guardian[™] Connect transmitter and paired to the Guardian[™] Connect app.
- Document time of insertion
- Calculate T=170 hours where the sensor may be removed at that time or after that time.
- Instruct trained subject to self-apply the sensor tape according to the user guide
- Instruct subject that sensors may be inserted on same side or opposite sides.
- Inform subjects that observation by sponsor may occur at any time during the study
- Review requirements and schedule study visit with subjects

10768467DOC Version C

- Review the visit date and time for YSI™* FST
- Remind subject to bring any medication, syringes, insulin, that might be needed to treat his/her diabetes during the YSI™* FST visit.
- Enter eCRFs into the study database as appropriate

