9.6. Replacement Sensors

In the event that a sensor connecting to the transmitter which pairs to the Guardian Connect app has failed/dislodged any time prior to YSI™* FST visit or within a duration of 5 hours YSI™* FST, the subject will be asked to replace both sensors with new inserted sensors. Any re-insertion of Guardian™ Sensor (3)s will be done only once and new transmitters will be connected to the new (replacement) sensors.

In the event that a sensor connecting to the transmitter, which functions as a glucose recorder, dislodges any time prior to YSI^{TM*} FST visit or within a duration of 5 hours YSI^{TM*} FST, the subject will continue to wear the remaining sensor for the duration of the subject's sensor wear time. A replaced sensor will not be issued to the subject.

Any YSI™* FST with a duration of 5 hours or more before sensor dislodgement will be considered complete and will not need to be rescheduled.

10768467DOC Version C

Page 52 of 97

Subjects will be issued replacement Guardian[™] Sensor (3)s to be inserted at in-clinic but at the date and time specified by the in-clinic.

Subject will wear the replaced sensors for 7 days and attempt to complete the required YSI™* FST visit.

Subjects will have their YSI™* FST visit rescheduled per the original randomly assigned FST Group.

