14.8.2. Pairing Scheme

All YSI^{™*} and fingerstick values collected will be presented. Descriptive analyses will include all YSI^{™*} values, such as those less than (<) 40 mg/dL, or greater than (>) 400 mg/dL as long as Guardian[™] Sensor (3) values are greater than or equal to (≥) 40 mg/dL or less than or equal to (≤) 400 mg/dL. Reference glucose values (YSI^{™*} values) will be paired with the closest Guardian[™] Sensor (3) value between [0, 5) minutes. Reference glucose values (fingerstick values) will be paired with the closest Guardian[™] Sensor (3) value between (-5, 0] minutes. The primary Guardian[™] Sensor (3) will be used as a reference for precision analysis and the pairing scheme will be [0, 5) minutes.

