14.10.2. Precision Analysis

Precision analysis will be performed for the two sensors worn by the same subject. Data from the primary GuardianTM Sensor (3) will be used as a reference. Data from sensor functioned as recorder will be reanalyzed using the exact calibration SMBG used for the primary sensor.

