7.7.2 Precision Analysis

Precision analysis will be performed for the two sensors worn by the same subject. This part of indicators will be summarized by descriptive statistics. The analysis method will be referred to section 7.2.

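### Precision is scored against the primary sensor, so paired ARD and the 20/20 label depend on which of two like sensors is designated primary; the effect is small and purely descriptive

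*Protocol*

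**What the plan says.** Protocol 5.2.2 names the two precision metrics, ARD and the 20/20 agreement rate, and ties the switch between limits to a reference glucose value: "Precision analysis including Absolute Relative Difference (ARD), and 20% agreement rate (±20 mg/dL (1.1 mmol/L) when Reference BG" is at or below 80 mg/dL. It does not say what the reference is when two sensors are compared.

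That is settled elsewhere. Protocol 14.8.2 says the primary sensor "will be used as a reference for precision analysis and the pairing scheme will be [0, 5) minutes", and SAP 6.6.2 repeats this. Protocol 14.10.2 agrees: "Data from the primary GuardianTM Sensor (3) will be used as a reference". It adds: "Data from sensor functioned as recorder will be reanalyzed using the exact calibration SMBG used for the primary sensor".

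The primary sensor is the one paired to the app (Protocol 5.2.1). On how it is selected, Protocol 9.2.4.1 says "It is up to investigator's discretion on which" sensor is paired. No random allocation of sensor or side is described.

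The two sensors are also treated differently after insertion. If the primary fails or dislodges before the FST or within its first 5 hours, both are replaced. If the recorder dislodges, "A replaced sensor will not be issued to the subject" (Protocol 9.6).

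SAP 7.7.2 gives no precision formula. It says "This part of indicators will be summarized by descriptive statistics" and refers to SAP 7.2, which covers demographic and baseline summaries. Neither document plans a symmetric measure or a repeat with the reference swapped.

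**The concern.** ARD and the 20/20 rule are designed for a test device against a trusted reference, here YSI. In the precision analysis a second sensor of the same model takes the reference role. Its reading becomes the ARD denominator, decides whether the ±20 mg/dL or the ±20% limit applies, and sets the width of the percentage limit. It carries the same kind of error as the sensor it is compared with.

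A measure of disagreement between two like devices should not change when their labels are exchanged. This one does. Dividing by a noisy value also tends to raise the mean, because pairs in which the primary happens to read low are given more weight. At stake is the clarity and reproducibility of the reported precision figures.

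**Working it through.** **Plan's own figure.** The documents give no expected value, threshold, sample size or power for precision, so there is nothing to reproduce.

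**Inputs from the documents.** The metrics (Protocol 5.2.2), the primary sensor as reference (Protocol 14.8.2, 14.10.2; SAP 6.6.2), and a MARD against YSI of 18%, which is the sample-size assumption in Protocol 14.5 and SAP 6.2.

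**Step 1: single pairs.** Planned ARD = |S1 − S2| / S_primary. Symmetric ARD = |S1 − S2| / ((S1 + S2)/2).

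| Readings (mg/dL) | Lower is primary | Higher is primary | Pair mean |
|---|---|---|---|
| 105, 130 | 25/105 = 23.8%, disagree | 25/130 = 19.2%, agree | 25/117.5 = 21.3%, disagree |
| 82, 100 | 18/82 = 22.0%, disagree | 18/100 = 18.0%, agree | 18/91 = 19.8%, agree |

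These pairs lie near the limit and were chosen to show the mechanism, not its frequency.

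**Step 2: average effect.** Assumptions not in the documents: S = T(1 + e); T lognormal with median 150 mg/dL and log-SD 0.4; e normal with SD = MARD/√(2/π); error correlation between sensors 0 or 0.5; both readings within 40–400 mg/dL; 1,000,000 pairs per setting.

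| MARD | Correlation | Mean ARD, primary | Mean ARD, pair mean | Difference (points) | 20/20 rate, primary | 20/20 rate, pair mean |
|---|---|---|---|---|---|---|
| 10% | 0 | 14.4 | 14.2 | 0.2 | 75.3 | 75.0 |
| 10% | 0.5 | 10.2 | 10.1 | 0.1 | 89.2 | 89.1 |
| 18% | 0 | 27.3 | 25.7 | 1.6 | 49.0 | 48.6 |
| 18% | 0.5 | 19.1 | 18.5 | 0.6 | 64.1 | 63.7 |

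Across these settings 6–9% of pairs change 20/20 label when the sensors are swapped. The changes balance: at MARD 18% and correlation 0.5, 4.27% of pairs agree only with sensor 1 as reference and 4.29% only with sensor 2.

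**Step 3: effect in one study.** A second model used 60 subjects with 28 pairs each (7 hours × 4 per hour), half of the error variance constant within a sensor, median glucose 160 mg/dL, MARD 9%, 12% or 18%, correlation 0 or 0.5, and 1,500 runs.

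- Moving from the primary to the pair mean changed mean paired ARD by 0.1 (9.2 to 9.1) to 1.6 points (27.4 to 25.8), and the 20/20 rate by 0.4 points or less.
- Swapping labels within a study moved mean paired ARD by a median of 0.1 to 1.2 points (95th percentile 0.4 to 3.6) and the 20/20 rate by a median of 0.6 to 0.8 points (95th percentile 1.7 to 2.4).
- Averaged over runs, the two labellings agreed to within 0.1 point.

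**Step 4: where the excess over MARD comes from.** In the second model at MARD 18% and correlation 0, the primary sensor's ARD against true glucose was 17.8 and paired ARD was 27.4. Dividing |S1 − S2| by true glucose gave 25.1. So 25.1 − 17.8 = 7.3 points come from having both sensors' errors in the numerator, and 27.4 − 25.1 = 2.3 points from the noisy denominator. The pair mean removes 27.4 − 25.8 = 1.6 of those 2.3. Over all settings the denominator adds 0.2 to 2.3 points.

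**The case against.** The strongest reply is that the choice is prespecified, consistent between protocol and SAP, and answers a coherent question: how far a second sensor departs from the one evaluated against YSI. The data streams are not fully exchangeable either, since the recorder is reprocessed with the primary's calibration values and is not replaced if it dislodges. Shared calibration also makes some error correlation plausible, so the 1.6-point case, which needs independent errors and a MARD of 18%, is the less likely end of the range. All of this stands and limits the size of the point. It does not turn the primary sensor into a reference standard or remove the dependence on the label.

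A reader might infer three stronger things that the documents do not support.

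- *The plan overstates disagreement in general.* This holds only for mean ARD. The 20/20 rate is equal or slightly better under the plan. Both sensors' errors belong in any between-sensor measure and stay in the numerator whatever the denominator.
- *The investigator's choice biases the result.* Protocol 9.2.4.1 places the choice at sensor insertion, and nothing links it to sensor performance. What is shown is arbitrary variation without a systematic direction.
- *The trial's conclusion is affected.* Precision is listed among the descriptive endpoints. Success rests only on criteria 1a to 1d, all of which compare the primary sensor with YSI (Protocol 14.9; SAP 7.6).

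**Conclusion.** The point holds and is minor. Paired ARD and the 20/20 label depend on which sensor is designated primary. Mean paired ARD is raised by about 0.1–0.2 points at an assumed MARD of 10% and 0.6–1.6 points at 18%. The 20/20 rate differs by 0.4 points or less, in the favourable direction, and label changes for individual pairs run equally both ways.

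The dependence on the label follows from the documents and arithmetic alone. The sizes rest on assumed normal relative errors, lognormal glucose, and error correlations of 0 and 0.5. The 10% MARD is also assumed, and the 18% is a planning value rather than a result.

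**What to change.** In Protocol 14.8.2 and 14.10.2 and SAP 6.6.2 and 7.7.2:

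- Define paired ARD as |S1 − S2| / ((S1 + S2)/2).
- Define paired agreement as within ±20 mg/dL when the pair mean is at or below 80 mg/dL, and otherwise within ±20% of the pair mean.
- Keep the primary-as-reference version as a second line.
- State that either figure reflects the errors of both sensors.

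SAP 7.7.2 needs an explicit formula in any case. The time-pairing window need not change.

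The cost is one definition and one line of code, with no new data. The drawback is that the headline figure would not be directly comparable with earlier reports that used one sensor as reference; the second line covers that.
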